3.2.7. Rationale for Including Genetic Testing

Genetic markers may be plausibly associated with SARS-CoV-2 acquisition. Recent studies indicate that ACE2 could be the host receptor for SARS-CoV-2. A number of ACE2 variants could reduce the association between ACE2 and SARS-CoV-2. Therefore, the expression of human ACE2 might be important for the susceptibility, symptoms, and outcome of SARS-CoV-2 infection [33]. The association between plausible genetic markers and SARS-CoV-2 infection and disease will be assessed in this study.

3.3. *Benefit/Risk Assessment*

COVID-19 can be unpredictable in its severity, but a 3.4% mortality rate has been observed among clinical pneumonia cases. The elderly (>60 years) and those with medical comorbidities are at highest risk of poor outcomes [1,2,3]. Moreover, transmission in younger persons amplifies infection in communities, putting susceptible persons at risk. There is no proven preventive drug other than transmission avoidance through barrier and droplet precautions, and in those likely exposed, quarantine for 14 days (beyond the viral incubation period) is currently recommended. HCQ has an excellent safety record at the proposed doses for 60 years and potent viral suppression *in vitro*. There is equipoise as to whether the *in vitro* efficacy of HCQ, or any other drug, will translate into preventive efficacy from disease or even a reduction in viral shedding. Thus, the potential benefit-to-risk ratio for testing HCQ as PEP is favorable in this population.

4. Objectives and Endpoints

Objectives	Endpoints
Primary	

 To test the efficacy of HCQ (400 mg orally daily for 3 days then 200 mg orally daily for an additional 11 days, to complete 14 days) to prevent incident SARS-CoV-2 infection, compared to ascorbic acid among contacts of persons with SARS-CoV-2 infection 	
 Polymerase chain reaction (PCR)-confirmed SARS-CoV-2 infection (self-collected samples collected daily Day 1 through Day 14)
Secondary	

 To determine the safety and tolerability of HCQ as SARS-CoV-2 PEP in adults 	
 Adverse events

 To test the efficacy of HCQ (400 mg orally daily for 3 days then 200 mg orally daily for an additional 11 days, to complete 14 days) to prevent incident SARS-CoV-2 infection 2 weeks after completing therapy, compared to ascorbic acid among contacts of persons with SARS-CoV-2 infection 	
 PCR-confirmed SARS-CoV-2 infection (self-collected samples collected daily Day 1 through Day 14 and collected 2 weeks after cessation of treatment [i.e., Day 28])

 To test the efficacy of HCQ to shorten the duration of SARS-CoV-2 shedding among those with SARS-CoV-2 infection in the HCQ PEP group 	
 SARS-CoV-2 viral shedding by PCR

 To test the efficacy of HCQ to prevent incident COVID-19 	
 PCR-confirmed COVID-19 diagnosis post start of HCQ therapy
Exploratory	

 To conduct SARS-CoV-2 viral genotyping to assess the impact of HCQ on viral resistance to HCQ PEP 	
 Viral genotyping of SARS-CoV-2 in a subset of treated study participants who develop infection

 To assess adherence to HCQ PEP 	
 Self-reported daily dosing and study therapy concentration (if in sub-study) in study participants

 • To evaluate the pharmacokinetics (PK) of HCQ by infection status 	
 • HCQ blood concentration

 • To assess if there is an association between PK of HCQ and the efficacy and safety endpoints evaluated 	
 • HCQ blood concentration, tolerability, and efficacy

 • To evaluate if SARS-CoV-2 viral load in the index case is associated with SARS-CoV-2 infection in the contact 	
 • SARS-CoV-2 semiquantitative PCR and genotyping

 • To test the efficacy of HCQ to shorten the magnitude of SARS-CoV-2 shedding among those with SARS-CoV-2 infection in the HCQ PEP group 	
 • Daily SARS-CoV-2 semiquantitative PCR

 • To investigate the association of plausible genetic markers and susceptibility to SARS-CoV-2 infection and/or severity of COVID-19 	
 • Rational gene candidates associated with SARS-CoV-2 infection and/or COVID-19 severity

COVID-19: coronavirus disease; HCQ: hydroxychloroquine; PEP: post-exposure prophylaxis; SARS-CoV-2: severe acute respiratory syndrome coronavirus 2.

5. Study Design

5.1. Overall Design

The overarching goal of this study is to assess the effectiveness of HCQ PEP on the incidence of SARS-CoV-2 detection by polymerase chain reaction (PCR) to inform public health control strategies.

This is a randomized, multi-center, placebo-equivalent (ascorbic acid) controlled, blinded study of the efficacy of HCQ PEP for the prevention of SARS-CoV-2 infection in adults exposed to the virus.

This study will enroll up to 2000 asymptomatic men and women 18 to 80 years of age (inclusive) at baseline who are close contacts of persons with PCR-confirmed SARS-CoV-2 or clinically suspected COVID-19 and a pending SARS-CoV-2 PCR test. Eligible participants will be enrolled and randomized 1:1 to HCQ or ascorbic acid at the level of the household (all eligible participants in 1 household will receive the same intervention).

Participants will be counseled about the preliminary *in vitro* data on HCQ activity against SARS-CoV-2 and equipoise regarding efficacy in humans.

Participants may participate in a sub-study where they will be asked to provide a dried blood spot (DBS) sample for therapy concentration and PK of HCQ as well as for SARS-CoV-2 antibody testing, if possible.

Index cases will be invited to participate in a sub-study where they will be asked to provide a mid-nasal swab at baseline and complete questionnaires at baseline and Day 28 to assess the extent to which SARS-CoV-2 transmission occurs within household contacts and whether that is dependent on the quantity of the virus shed.

An independent data and safety monitoring board (DSMB) will be convened for this study with expertise in COVID-19 or respiratory viruses, PEP, and emerging epidemics; DSMB will include a biostatistician. The purpose of the DSMB is to monitor the study for operational futility, social harms, and efficacy.

This multi-center study will be conducted in high COVID-19 incidence areas in the United States. At the time of the writing of this document, the sites are expected to be western Washington (Snohomish, King, and Pierce counties) and New York, NY. As of 13 March 2020, there are 328 cases and 32 deaths in King County, most of them in Seattle. As of 13 March 2020, there are 158 cases in New York City. Both settings are urban areas; Seattle has a population of 3.5 million and New York has 8.6 million.

If additional data emerge on alternative effective agents for SARS-CoV-2 prophylaxis and/or data about HCQ as PEP, the protocol could be modified through an amendment to alter its sample size and evaluate an alternative therapy as PEP. Alternatively, this platform study could be modified through an adaptive design to test the efficacy of new potential agents for COVID-19 PEP.

5.2. *Participant and Study Completion*

Up to 2000 participants will be randomly assigned to study treatment. *Up to 2000 index cases will be enrolled.*

A participant is considered to have completed the study if he/she has completed all phases of the study including the last scheduled procedure shown in the Schedule of Activities (SoA).

This study will be considered completed when sufficient number of participants complete the study to enable appropriate evaluation of the primary endpoint.

6. Study Population

Prospective approval of protocol deviations to recruitment and enrollment criteria, also known as protocol waivers or exemptions, is not permitted.

6.1. Close Contact Participants

6.1.1. Inclusion Criteria

Participants are eligible to be included in the study only if all of the following criteria apply:

1. Men or women 18 to 80 years of age inclusive, at the time of signing the informed consent
2. Willing and able to provide informed consent
3. Had a close contact of a person (index) with known PCR-confirmed SARS-CoV-2 infection or index who is currently being assessed for COVID-19

Close contact is defined as:

- a. Household contact (i.e., residing with the index case in the 14 days prior to index diagnosis or prolonged exposure within a residence/vehicle/enclosed space without maintaining social distance)
 - b. Medical staff, first responders, or other care persons who cared for the index case without personal protection (mask and gloves)
4. Less than 4 days since last exposure (close contact with a person with SARS-CoV-2 infection) to the index case
 5. Access to device and internet for Telehealth visits
 6. Not planning to take HCQ in addition to the study medication

6.1.2. Exclusion Criteria

Participants are excluded from the study if any of the following criteria apply:

1. Known hypersensitivity to HCQ or other 4-aminoquinoline compounds
2. Currently hospitalized
3. Symptomatic with subjective fever, cough, or shortness of breath
4. Current medications exclude concomitant use of HCQ
5. Concomitant use of other anti-malarial treatment or chemoprophylaxis, including chloroquine, mefloquine, artemether, or lumefantrine.
6. History of retinopathy of any etiology
7. Psoriasis
8. Porphyria
9. Known bone marrow disorders with significant neutropenia (polymorphonuclear leukocytes <1500) or thrombocytopenia (<100 K)
10. Concomitant use of digoxin, cyclosporin, cimetidine, amiodarone, or tamoxifen
11. Known moderate or severe liver disease
12. Known long QT syndrome
13. Severe renal impairment

14. Use of any investigational or non-registered drug or vaccine within 30 days preceding the first dose of the study drugs or planned use during the study period

6.2. *Index Cases*

6.2.1. *Inclusion Criteria*

1. Men or women ≥ 18 years of age inclusive, at the time of signing the informed consent
2. Willing and able to provide informed consent
3. Currently diagnosed with known PCR-confirmed SARS-CoV-2 infection or is currently being assessed for COVID-19
4. A close contact is enrolled in the study

6.2.2. *Exclusion Criteria*

1. Currently hospitalized

6.3. *Screen Failures*

Screen failures are defined as participants who consent to participate in the clinical study but are not subsequently randomly assigned to study treatment. A minimal set of screen failure information is required to ensure transparent reporting of screen failure participants to meet the Consolidated Standards of Reporting Trials publishing requirements and to respond to queries from regulatory authorities. Minimal information includes demography, screen failure details, eligibility criteria, and any serious adverse event (SAE).

Individuals who do not meet the criteria for participation in this study (screen failure) can be rescreened if there is a change in their eligibility.

6.4. *Recruitment*

Each site will establish local recruitment and screening methods that operationalize protocol-specified requirements for eligibility determination in a manner that is tailored to and most efficient for the local study setting and target study population. Each site will use a variety of recruitment approaches, including direct recruitment at clinics, referrals from other providers and SARS-CoV-2 testing sites and laboratories, and use of online and social networking websites and apps. Recruitment materials will educate participants about COVID-19, transmission within households, epidemiology in the community, and the *in vitro* data on HCQ limiting SARS-CoV-2 cell entry.

Initially, the study will enroll from 2 clinical sites: western Washington and New York, which have established track records of high quality clinical research integrated into clinical care settings; annual retention rates in clinical trials conducted in these sites exceed 80% to 90%. The sites have large COVID-19 epidemics with regulation limiting contact to reduce infectious spread.

6.5. *Co-enrollment Guidelines*

Close contact participants may be co-enrolled in other research studies, provided that these are observational studies only. Any other exception requires approval of the Co-Principal

Investigators. The study team should be consulted for co-enrollment in studies that do not meet this guidance or if there are questions about eligibility for co-enrollment. For any co-enrolled study, combined blood draws should not exceed current Red Cross phlebotomy guidance.

Index case participants may enroll at any point in another study.

7. Treatments

Study treatment is defined as any investigational treatment(s), marketed product(s), placebo, or medical device(s) intended to be administered to a study participant according to the study protocol.

7.1. *Treatments Administered*

Study Treatment Name	Hydroxychloroquine sulfate	Ascorbic acid
Dosage Formulation	200 mg (155 mg base) tablets	250 mg tablets
Route of Administration	Oral	
Dosing Instructions	Take 2 tablets for the first 3 days and 1 tablet for the subsequent 11 days, for a total of 14 days of treatment. Take at approximately the same time of the day with a meal or a glass of milk. If a dose is missed, it should be taken as soon as possible. If it is less than 4 hours before the next dose, the dose should be skipped.	
Packaging and Labeling	The medication for home delivery will be dispensed in an unmarked container with the study label. The container will be labeled with a unique identifier. The container will be packed in a standard box used for mail delivery of medications as needed.	
Manufacturer	To be determined	To be determined

7.2. *Risks to the Participants*

7.2.1. *Risks Associated with PEP Administration with HCQ*

The risks associated with PEP reflect the adverse events (AEs) related to HCQ administration. With tens of millions of doses administered for malaria and autoimmune diseases, the side effect profile of HCQ is well described and the drug is generally well tolerated. With short-term administration (as opposed to chronic/year-long use in rheumatologic disease management), the major AEs are gastrointestinal (nausea, vomiting, dyspepsia, abdominal cramps, and diarrhea) and transient skin rashes. The gastrointestinal symptoms may vary by specific generic manufacturer of HCQ [35] and are best managed by taking the drug with food or a glass of milk (Appendix 6). A transient rash, most commonly morbilliform or psoriasiform, can develop in 10% of participants, often with a sustained loading dose, and is often managed by lowering the dose. To avoid this potential side effect, this protocol is using a short loading dose, not a sustained one. Uncommonly, idiosyncratic leukopenia/thrombocytopenia can occur and the drug

should not be given to those with underlying bone marrow disorders. Lastly, hypoglycemia can occur and those taking insulin or glucose-lowering drugs are at risk; blood glucose should be monitored.

Minor blurry vision may occur with acute HCQ use, is reversible, dose-related, and is generally not severe. It may also be associated with mild headaches. It is caused by deposition of HCQ in the cornea or ocular muscle weakness, and is not a predictor of long-term toxicity. Participants experiencing minor blurry vision may adjust to it with counselling and reassurance that it is reversible and not progressive.

More severe rashes, including drug-related eosinophilia with systemic symptoms and Stevens-Johnson syndrome occur rarely.

Long-term manifestations of HCQ, including retinitis, renal and hepatic disease, and cardiomyopathy ([Appendix 4](#)), are not likely in this 2-week PEP exposure.

7.2.2. *Risks Associated with COVID-19 Surveillance and Quarantine*

Enrollment in this protocol will not impact the public health department's advice for self-quarantine. That said, quarantine is known to be stressful, especially for healthcare workers. Enrollment may improve morale during public health quarantine. Since there is clinical equipoise regarding HCQ efficacy on viral shedding, participants will be counseled to follow recommendations for self-quarantine.

7.3. *Strategies to Minimize Risk*

7.3.1. *Dose Selection*

The recommended dose of HCQ for chronic use in lupus erythematosus is 200 mg to 400 mg daily—a dose that is safely taken for years including among elderly patients (≥ 65 years). The selection of 400 mg for 3 days then 200 mg daily for 11 days is likely to be safe with transient AEs (gastrointestinal symptoms and rashes) that are self-remitting.

7.3.2. *Management of Participants to Limit Risks of SARS-CoV-2 Transmission*

To limit the transmission of SARS-CoV-2, participants will receive visits via secure Telehealth in order to limit the movement of persons with potential SARS-CoV-2 and leave clinical space free for patients seeking care. Also, to limit exposure in waiting rooms and pharmacies, clinical specimens will be self-collected and medications delivered to homes.

7.4. *Dose Modification and Toxicity Management*

If a study therapy dose is missed, it should be taken as soon as possible. If it is less than 4 hours before the next dose, the dose should be skipped.

Modification for toxicities is discussed below. Only toxicities related to study medications provided through the study will be considered in the toxicity management section.

Grade 1 or 2

Participants who develop Grade 1 or 2 toxicity (per division of acquired immunodeficiency syndrome [DAIDS] adverse event [AE] Grading Table; see: <https://rsc.tech->

[res.com/docs/default-source/safety/division-of-aids-\(daids\)-table-for-grading-the-severity-of-adult-and-pediatric-adverse-events-corrected-v-2-1.pdf](https://res.com/docs/default-source/safety/division-of-aids-(daids)-table-for-grading-the-severity-of-adult-and-pediatric-adverse-events-corrected-v-2-1.pdf)) that is considered to be related to study medication may continue study treatment at the discretion of the site Investigator with close follow-up. If a participant chooses to discontinue study treatment, the site should notify the study protocol team within 7 days. These participants will remain on study, off study treatment, and have all evaluations performed.

Grade 3

- Participants who develop a Grade 3 symptomatic toxicity thought by the site Investigator to be related to study drug should have HCQ PEP withheld, and the site should consult with the Core Protocol team. The participant should be reevaluated every 2 days until the AE returns to Grade ≤ 2 , at which time study drug may be reintroduced at the discretion of the site Investigator in consultation with the protocol team.
- Participants experiencing Grade 3 toxicity requiring permanent discontinuation of study medication should be followed up weekly until resolution of the toxicity. Participants will have premature study treatment discontinuation evaluations performed. These participants will remain on study, off study treatment, and have all evaluations performed per the SoA.

Grade 4

- Participants who develop a Grade 4 symptomatic toxicity will have study medication permanently discontinued, and the site should notify study team within 48 hours.
- Participants experiencing Grade 4 toxicity requiring permanent discontinuation of HCQ PEP should be followed up weekly until resolution of the AE or return to baseline. These participants will remain on study, off study treatment, and have all evaluations performed per the SoA.

Specific Management of Toxicities Related to Study-Provided Drugs

Gastrointestinal disturbance

Gastrointestinal disturbance (nausea, vomiting, diarrhea) is a common known possible side effect of HCQ. Dividing doses by 6 hours and taking with food or milk may improve tolerability.

Visual disturbances

Suspected visual changes should be evaluated for possible etiologies. Participants experiencing Grade 1 or Grade 2 vision changes may continue use, at the discretion of the site Investigator. Participants who develop a Grade 3 symptomatic toxicity thought by the site Investigator to be related to study drug should have HCQ PEP withheld, and the site should consult with the Core Protocol team. The participant should be reevaluated every 2 days until the AE returns to Grade ≤ 2 , at which time study drug may be reintroduced at the discretion of the site Investigator in consultation with the protocol team.

Allergic reactions

HCQ should be discontinued permanently if a serious allergic reaction is suspected. These participants will remain on study, off study treatment, and have all evaluations performed per the standard operating procedure(s).

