7.5. Method of Treatment Assignment

Participants will be randomized in a 1:1 ratio to HCQ or ascorbic acid at the level of the household (all eligible participants in 1 household will receive the same intervention). The randomization plan will be written by the Study Statistician.

The randomization code and resulting allocation list will be generated and maintained by the Study Statistician. The list will be blocked and stratified by site and contact type (household versus healthcare worker).

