8.1. Discontinuation of Study Treatment

Study treatment will be discontinued for the following reasons:

- Requirement for prohibited concomitant medications or other contraindication to HCQ
- Occurrence of an AE requiring discontinuation of study medication
- Request by participant to terminate study treatment
- Clinical reasons believed to be life-threatening by the physician, even if not addressed in [Section 7.2](#)

Participants who stop study treatment should continue study participation off study medication with continued evaluations as per the SoA. The reason for study medication discontinuation should be recorded.

Participants who are identified as SARS-CoV-2 positive by PCR at baseline should continue study therapy and study participation.

Participants with a clinical diagnosis of COVID-19 should continue on study therapy unless they are started on COVID-19 treatment outside of the study.

8.2. *Withdrawal from the Study*

- A participant may withdraw from the study at any time at his/her own request or may be withdrawn at any time for the following reasons:
 - At the request of the primary care provider if he/she thinks the study is no longer in the best interest of the participant
 - Participant is judged by the Investigator to be at significant risk of failing to comply with the provisions of the protocol as to cause harm to self or seriously interfere with the validity of the study results
 - At the discretion of the Institutional Review Board/Ethics Committee or government agencies as part of their duties, Investigator, or industry supporter
- If the participant withdraws consent for disclosure of future information, the sponsor may retain and continue to use any data collected before such withdrawal of consent.
- If a participant withdraws from the study, he/she may request destruction of any samples taken and not tested, and the Investigator must document this in the site study records.
- See SoA for data to be collected at the time of study discontinuation and follow-up and for any further evaluations that need to be completed.

8.3. *Lost to Follow-up*

A participant will be considered lost to follow-up if he/she is unable to be contacted by the study site.

The following actions must be taken if a participant fails to comply with required study procedures:

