- The site must attempt to contact the participant as soon as possible and counsel the participant on the importance of maintaining the assigned procedure schedule and ascertain whether or not the participant wishes to and/or should continue in the study.
- Before a participant is deemed lost to follow-up, the Investigator or designee must make every effort to regain contact with the participant (where possible, 3 telephone calls and, if necessary, a certified letter to the participant's last known mailing address or local equivalent methods). These contact attempts should be documented in the participant's medical record.
- Should the participant continue to be unreachable, he/she will be considered to have withdrawn from the study with a primary reason of lost to follow-up.

9. *Study Encounters*

The current COVID-19 pandemic has placed a significant burden on the healthcare system. For this study, specimen and data collection will be conducted to minimize impact of non-ill participants within the healthcare system. If the participant is assessed as eligible, contact between study participants and study personnel will occur via a Health Insurance Portability and Accountability Act (HIPAA)-compliant video conference (Telehealth), although in-person visits either at the participant's home or at a research center are permitted.

Participants will be instructed to seek clinical care should they manifest any signs or symptoms of COVID-19.

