9.1. Close Contact Participants

9.1.1. Screening/Baseline Evaluation: Day 0/1

Participants will be assessed for study eligibility through a screening conducted through a web-based screening tool, HIPAA-compliant video conference (Telehealth), telephone, or text messaging.

Day 0 evaluations are as follows:

- Informed consent
- Collection of demographic information
- Collection of past and current medical conditions, including known pregnancy and/or lactation status
- Collection of concomitant medication information
- Collection of information regarding exposure to the index case
- Check of inclusion and exclusion criteria

Eligible participants will be randomized with all members of a household assigned to the same arm. Participants will receive a swab kit either via courier or mail, which includes a Quick Start Instruction Card, swabs, plastic tubes for swab collection, and a return box with affixed Category B UN3373 label, as required by International Air Transport Association (IATA) guidelines [36].

The participant will do the following on Day 1:

- Collect mid-nasal swab for PCR
- Take study therapy (HCQ or ascorbic acid, as assigned)
- Complete Daily Survey (online, Telehealth, telephone, or text messaging). This Survey will include confirmation of adherence to study therapy dosing and daily swab collection, concomitant medication review, and symptoms review.
- *If in DBS Sub-study, collect DBS samples for analysis of anti-SARS-CoV-2 antibodies (if possible).*

Instructions for skin puncture and DBS sample preparation are provided in [Appendix 6](#). A study team member will be available via Telehealth, telephone, or text messaging to provide support for completion of this study procedure.

Screening/Day 0 and Day 1 procedures may occur on the same day.

The index case SARS-CoV-2 positive test results will be confirmed through self-report of the contact participant. *If in the index case sub-study, shedding of SARS-CoV-2 will be assessed by PCR of a mid-nasal swab ([Section 9.2](#)).*

9.1.2. Day 2 Through Day 13

The participant will do the following every day from Day 1 through Day 13, inclusive:

- Collect mid-nasal swab for PCR
- Take study therapy (HCQ or ascorbic acid, as assigned)
- Complete Daily Survey (online, telephone, or text messaging). This Survey will include confirmation of adherence to study therapy dosing and daily swab collection, concomitant medication review, and symptoms review.

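### Exclusion criterion 9 admits a contact with a known bone marrow disorder unless counts are low, while Protocol 7.2.1 says, with no count threshold, that HCQ should be withheld from such people

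*Protocol*

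**What the plan says.** Protocol 6.1.2, criterion 9, excludes "Known bone marrow disorders with significant neutropenia (polymorphonuclear leukocytes <1500) or thrombocytopenia (<100 K".

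Protocol 7.2.1 mentions uncommon, idiosyncratic falls in white cells or platelets on HCQ. The same sentence goes on to say that the drug "should not be given to those with underlying bone marrow disorders". It attaches no count threshold.

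Four other places bear on the point:

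- Section 6 closes the list to exceptions: "Prospective approval of protocol deviations to recruitment and enrollment criteria, also known as protocol waivers or exemptions, is not permitted".
- Section 7.5 sets the allocation: "Participants will be randomized in a 1:1 ratio to HCQ or ascorbic acid at the level of the household".
- Section 8.1 gives as one reason to stop study treatment: "Requirement for prohibited concomitant medications or other contraindication to HCQ".
- Section 9.1.1 lists among the Day 0 evaluations: "Collection of past and current medical conditions, including known pregnancy and/or lactation status".

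**The concern.** Two current parts of the protocol give different answers for the same person. Take a contact who reports a marrow disorder and has adequate counts, or has no recent count. The eligibility list lets this contact in, and the risk section says not to give the drug. A site that follows the list exactly can randomize someone whom the protocol itself says should not receive one of the two treatments.

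What is at stake is the safety of those few participants and the consistency of the entry rule. The efficacy comparison is not at stake.

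**Working it through.** No figure in the plan depends on this, so the check is a comparison of texts.

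**Step 1: list the cases.** Let D be a known bone marrow disorder, N neutrophils known to be below 1500, and T platelets known to be below 100 K. Criterion 9 can be parsed in two ways:

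- Reading A: D and (N or T).
- Reading B: (D and N), or T alone.

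Section 7.2.1 withholds HCQ whenever D holds.

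| D | N | T | Excluded, reading A | Excluded, reading B | 7.2.1 withholds HCQ |
|---|---|---|---|---|---|
| yes | no | no | no | no | **yes** |
| yes | yes | no | yes | yes | yes |
| yes | no | yes | yes | yes | yes |
| yes | yes | yes | yes | yes | yes |
| no | yes | no | no | no | no |
| no | no | yes | no | yes | no |
| no | yes | yes | no | yes | no |
| no | no | no | no | no | no |

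The first row is the mismatch, and it appears under both readings. It includes people whose counts are simply unknown.

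**Step 2: look for another entry rule that covers the first row.** Criterion 1 concerns hypersensitivity and criterion 4 concerns medications. The remaining criteria name other conditions, drugs or circumstances. None covers a marrow disorder with adequate or unknown counts.

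**Step 3: look for a rule outside the entry criteria.** Section 8.1 could lead a clinician to stop treatment for a contraindication, but it governs discontinuation, not entry, and does not name marrow disorders. Section 10 requires baseline evaluations to be reviewed, but against the same eligibility list.

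**Step 4: ask where the counts would come from.** The Schedule of Activities has no blood count at screening. Section 10 confines blood collection to a sub-study, and section 10.4 gives its purpose as drug concentration, pharmacokinetics and possibly antibodies. Section 9 says in-person visits at "home or at a research center are permitted", but no count is scheduled at them. The limits in criterion 9 can therefore be applied only from counts the contact already knows or has on record.

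**Step 5: size.** Under 1:1 allocation, each such contact who is enrolled has a probability of 0.5 of receiving HCQ. How many would be enrolled cannot be derived, because neither document gives a prevalence. SAP section 6 lists chronic hematologic disease as a baseline condition, so blood disorders in general are not assumed absent, but that category is not the same as a marrow disorder.

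**Step 6: effect on the statistics.** Changing criterion 9 acts before randomization. The targets in SAP 2.4 (93 events; 1240 participants negative at baseline) stay as they are, so power and type I error do not change.

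**The case against.** The strongest reply is that 7.2.1 is a short account of drug risks and criterion 9 is its working form. Both address low white cells and platelets, and criterion 9 supplies the limits. Section 7.2.1 also says blood glucose should be monitored in people on glucose-lowering drugs. Yet no glucose test is scheduled, and 7.9.2 treats antidiabetic agents only as precautionary. Not every caution in 7.2.1 becomes a trial rule.

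This reading is possible, but the protocol does not state it. The wording for marrow disorders is that of withholding the drug, whereas the wording for glucose is that of monitoring. If the thresholds were meant to limit 7.2.1, it should say so, and that too would need an edit.

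Other parts of the reply stand:

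- The bar on waivers does not oblige a site to enroll everyone who passes the list. A clinician may decline such a contact. The list permits enrollment but does not force it.
- Section 8.1 limits exposure. The history is taken at Day 0 and section 7.6 has drug dispensed 24 to 48 hours after enrollment, so a site that treats 7.2.1 as a contraindication could act before or soon after the first dose.
- A reader might infer that criterion 9 leaves these people without hematologic monitoring. The documents do not support tying that to this criterion. The absence of scheduled counts applies to every participant, as do the toxicity rules in 7.4, for example "Participants who develop a Grade 4 symptomatic toxicity will have study medication permanently discontinued". Changing criterion 9 would alter neither.
- A reader might turn the 1:1 allocation into a probability that some such contact receives HCQ. That needs an assumed number of such contacts, and it would measure exposure, not harm.
- Whether HCQ must be withheld when counts are adequate may depend on the drug label. Appendix 4 refers to the label, but its text is not in the documents reviewed, so nothing here rests on it.

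**Conclusion.** The mismatch is real under either reading of criterion 9, and it is minor. It is an inconsistency between the entry rule and the protocol's own risk statement, affecting an unknown and probably small number of contacts.

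Confidence is high on the textual conflict. It is lower on clinical consequence, because the documents give no risk estimate for people with a marrow disorder and adequate counts, only that the blood effects are uncommon. The conclusion assumes that 7.2.1 means what it says without an implied threshold, and that sites apply the entry list as written.

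**What to change.** Reword criterion 9 as two separate exclusions:

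1. Any known bone marrow disorder, whatever the counts, judged from the Day 0 medical history.
2. Known significant neutropenia (neutrophils below 1500) or thrombocytopenia (platelets below 100 K).

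The second clause is needed because, under reading B, platelets below 100 K already exclude a contact with no marrow disorder. Simply cutting criterion 9 back to marrow disorders would remove that exclusion. The two clauses together exclude every row of the table except the last, so nothing is loosened. They do widen the rule slightly: under reading A, contacts with known low counts and no marrow disorder also become ineligible; under reading B, only those with known low neutrophils alone are added.

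No new test is required. Criteria 7 and 8 (psoriasis, porphyria) already exclude on history alone.

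The alternative is to put the same thresholds into 7.2.1. That also removes the mismatch, but with no count scheduled at screening the plan would then need to say where the counts come from. Excluding on history is simpler and more cautious.

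The cost is one line in an amendment and in the screening tool. A few more contacts become ineligible and are replaced at recruitment.
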